3.1. Statistical Analysis Environment

Statistical analysis software: SAS Institute Inc., SAS for Windows Version 9.2 or higher

The version of SAS used for summarization and analysis will be defined in the written statistical analysis specification.

3.2. Testing

When any test is applied, a two-sided level of significance of 5% will be used without correction for continuity or adjustment of multiplicity.

P-values will be displayed with two asterisks (**) when being larger than 0 (zero) and less than 0.01 and with one asterisk (*) when being greater than or equal to 0.01 and less than 0.05. For any unknown/unspecified value, its frequency will be displayed in the tabulation, but it will not be included in the calculation for testing.

3.3. Policy regarding Categorization

Unknown values, unspecified values, and calculation items that cannot be calculated will be summarized together as “unknown/unspecified.”

3.4. Handling of Adverse Events

In the summarization of the number of adverse events (adverse drug reactions) by PT, if the same patient experiences any adverse event (adverse drug reaction) of the same PT multiple times, each event will be counted once (number of events basis). In the summarization of the number of patients with adverse events (adverse drug reactions) by SOC or PT, if the same patient experiences any adverse event (adverse drug reaction) of the same SOC or PT multiple times, the patient will be counted once (number of patients basis).

Adverse events (adverse drug reactions) will be summarized using the “ICH International Medical Dictionary for Regulatory Activities Japanese Version (MedDRA/J)” according to the notification concerning the “ICH International Medical Dictionary for Regulatory Activities Japanese Version (MedDRA/J)” (Notification No. 0325001 of the Safety Division, Pharmaceutical and Food Safety Bureau, MHLW, and Notification No. 0325032 of the Evaluation and Licensing Division, Pharmaceutical and Food Safety Bureau, MHLW, dated March 25, 2004).

The version of the MedDRA/J used for summarization and analysis will be defined in the written statistical analysis specification.

The procedure for summarization and analysis through grouping of MedDRA terms by SOC is as follows:

- According to the LLT entered (coded) in the database, the MedDRA table of the above version will be referenced to follow the link for each adverse event and combine the LLT with the information on “PT-SOC” of the version.

- Adverse event terms will be output in the ascending order of the SOC internationally agreed order-PT codes.

3.5. Rules about Calculation Methods for Individual Items, Units, and Number of Digits Displayed

Item	Unit	Digits displayed	Calculation method, etc.
Calculation of durations (duration to discontinuation, duration to onset of adverse drug reaction, duration of treatment)	day	1	End date – Start date + 1 (including the start date) 1 year = 52 weeks = 364 days
Age	years old	1	INT ([Start date of treatment with Lipacreon – Date of birth + 1)/365.25)
P-value	-	0.001	All numbers after the third decimal place will be disregarded.
Incidence	-	0.01	
Effectiveness rate	-	0.1	Evaluation of the degree of overall improvement: Number of improved patients/(No. of improved patients + No. of unchanged patients + No. of deteriorated patients) × 100
Summary statistics	-	-	Sample size: Integral number Minimum and maximum values: Displayed in the number of digits of the raw data. Other statistics: The two lower digits of the raw data will be rounded off to display up to the lowest digit of the raw data.

3.6. Allowable Time Window for Each Evaluation Time Point

The allowable time window for each evaluation time point is as shown below. If multiple evaluation values exist within an allowable time window, the evaluation value obtained at the time point with the smallest difference in time (absolute value) from the specified evaluation date will be adopted. If the differences in time are the same, the evaluation value obtained after the specified evaluation date will be adopted. The number of days from the start date of treatment with Lipacreon will be calculated with the start date of treatment with Lipacreon being deemed as Day 1 and the date before the start of treatment with Lipacreon being deemed as –Day 1.

Nutritional endpoints, symptoms of exocrine pancreatic insufficiency:

Evaluation time point	Allowable time window ^{*1}	Specified evaluation date ^{*1}
Before the start of treatment	to Day 1	Day 1
At Week 4	Day 14 to Day 41	Day 28
At Week 8	Day 56±14	Day 56
At Week 24	Day 168±28	Day 168
At Week 52	Day 364±28	Day 364
At Year X $2 \leq X \leq 7$	$364 \times \text{Day } X \pm 28$	$364 \times X$
Before dose increase ^{*2}	Start date of dose increase – 28 days to Start date of dose increase	Start date of dose increase
At the time of discontinuation	Date of discontinuation – 28 days to Date of discontinuation, which does not correspond to any of the above	Date of discontinuation

At the time of last evaluation	Data obtained on the last date among the data obtained before Day $364 \times X + 28$	
--------------------------------	---	--

Degree of overall improvement:

Evaluation time point	Allowable time window ^{*1}	Specified evaluation date ^{*1}
At Week 24	Day 168±28	Day 168
At Week 52	Day 364± 28	Day 364
At the time of discontinuation	Date of discontinuation – 28 days to Date of discontinuation, which does not correspond to any of the above	Date of discontinuation
At the time of last evaluation	All of the last dates	

*1: The allowable time window and the specified evaluation date before the start of treatment to Year X are displayed in the number of days from the start date of treatment with Lipacreon.

*2: A dose increase will be defined as a dose of ≥ 1800 mg/day administered.

4. Statistical Analyses

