 - ⑤ Start date of administration,
- 3) In case any patient who had been administered with LipaCreon were enrolled, the information before the enrollment is to be collected as much as possible if it is required in the registry items.

(3) Observation Period

The observation period for a case is at least 52 weeks from the start of administration of LipaCreon. Even if the administration period exceeded 52 weeks, the assessment is to be done at the time of 52nd weeks. After 52nd week, administration status, concomitant use drug status, nutritious assessment items, symptoms relating to pancreatic excretion insufficiency and adverse events should be described in the Follow-up Case Report Form, and it should be submitted to the sponsor company.

(4) Description and submission of the Case Report Form

In this Registry, the Case Report Form is consisted of seven report brochures. After each whole follow-up period per case is completed, follow-up items should be fulfilled on all the registered cases (incl. discontinued cases). After all items were fulfilled, final confirmation date

should be written, signature should be done, and seal should be done before submission.

The Case Report Form (1): From the first administration date to 52nd week

The Case Report Form (2) – (7): After 52nd administration, one CRF per year

(5) Discontinued cases

In this Registry, the cases which the administration was discontinued during the observation period, or which follow-up became impossible due to patient's visit stopped, or other reasons, will be handled as "discontinued cases". For these discontinued cases, stopped date, reason of stopping, assessment done until the discontinuation should be written in the forms.

7. Planned registry period

Planned registry period: From the release of Lipa Creon to 31st March 2018

Case registration period: From the release of Lipa Creon to 31st March 2017

Observation period: For 52 weeks from the start of administration of LipaCreon. Even if the administration period exceeded 52 weeks, the assessment is to be done at the time of 52nd weeks.

Follow-up period: After the 52nd week, administration status, concomitant use drug status, nutritious assessment items, symptoms relating to pancreatic excretion insufficiency and adverse events should be described in the Follow-up Case Report Form annually, and it should be submitted to the company.

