1.2. Outline of the Survey

Brand name: Lipacreon® Granules 300 mg Sachets, Lipacreon® Capsules 150 mg

Survey name: Special Drug Use-Results Survey

CF all-case surveillance: P12-893/LPC02T

Special Drug Use-Results Survey (all-case surveillance) —All-Case Surveillance in Patients with Exocrine Pancreatic Insufficiency due to Cystic Fibrosis of the Pancreas—

Date of approval: April 22, 2011

Date of designation: April 14, 2011

End date of the re-examination period: April 21, 2019

Survey period: August 30, 2011 through March 31, 2018

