36	Initial daily dose (mg/day)	The initial daily dose will be determined based on the daily dose on the start date of treatment with Lipacreen. <900, 900, >900 and <1800, 1800, >1800, unknown/unspecified

No	Patient demographic factor	Description
37	Mean daily dose (safety) (mg/day)	
The mean daily dose will be determined based on the mean daily dose (safety). <900, 900, >900 and <1800, 1800, >1800, unknown/unspecified
 
The mean daily dose for each dose observation period will be determined based on the mean daily doses during the individual periods shown below.
 
Dose observation periods:
 
 At the start of treatment: Day 1 At Week 2: Day 2 to Day 14 At Week 4: Day 15 to Day 28 At Week 8: Day 29 to Day 56 At Week 16: Day 57 to Day 112 At Week 24: Day 113 to Day 168 At Week 32: Day 169 to Day 224 At Week 40: Day 225 to Day 280 At Week 48: Day 281 to Day 336 At Week 52: Day 337 to Day 364 At Year 2: Day 365 to Day 728 At Year 3: Day 729 to Day 1092 At Year 4: Day 1093 to Day 1456 At Year 5: Day 1457 to Day 1820 At Year 6: Day 1821 to Day 2184 At Year 7: Day 2185 to Day 2400

No	Indicator of treatment status	Description
38	Mean daily dose (effectiveness rate) (mg/day)	
The mean daily dose will be determined based on the mean daily dose (effectiveness rate). <900, 900, >900 and <1800, 1800, >1800, unknown/unspecified
 
The mean daily dose for each dose observation period will be determined based on the mean daily doses during the individual periods shown below.
 
Dose observation periods:
 
 At the start of treatment: Day 1 At Week 2: Day 2 to Day 14 At Week 4: Day 15 to Day 28 At Week 8: Day 29 to Day 56 At Week 16: Day 57 to Day 112 At Week 24: Day 113 to Day 168 At Week 32: Day 169 to Day 224 At Week 40: Day 225 to Day 280 At Week 48: Day 281 to Day 336 At Week 52: Day 337 to Day 364

No	Indicator of treatment status	Description
39	Maximum daily dose (safety) (mg/day)	
The maximum daily dose will be determined based on the maximum value of the daily dose during the duration of use of Lipacreon (safety). <900, 900, >900 and <1800, 1800, >1800, unknown/unspecified
 
In the summarization for the occurrence status of adverse events and adverse drug reactions, the maximum daily dose in a patient experiencing an adverse event or adverse drug reaction will be determined based on the maximum daily dose until the time of initial onset of the event.

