4.1.1.3. Breakdown of patient composition

The following will be presented: the number of institutions surveyed, the number of patients registered in the survey, the number of patients with available case report forms, the number of patients with no available case report forms, the number of patients included in the safety analysis, the number of patients excluded from the safety analysis, the number of patients included in the effectiveness analysis, the number of patients excluded from the effectiveness analysis, the number of patients included in the effectiveness analysis (patients completing the 52-week treatment), and the number of patients not completing the 52-week treatment. For patients excluded from the safety analysis and patients excluded from the effectiveness analysis, the number of the individual patients will be presented by reason for exclusion (Figure 1.1.3.1).

In addition, the number of patients with available case report forms will be presented by separate volume (Figure 1.1.3.2).

For patients with multiple reasons for exclusion among the patients excluded from the safety analysis or patients excluded from the effectiveness analysis, a list of patients will be prepared (Table 1.1.3.1, Table 1.1.3.2).

For patients excluded from the safety analysis, lists of reported adverse events will be prepared by SOC, PT, seriousness, and presence/absence of relationship (Table 1.1.3.3).

For discontinued patients, a list of patients will be prepared by survey-participating institution (Table 1.1.3.4).

No	Item name	Contents to be displayed
1	Survey-participating institution	-
2	Department name	-
3	Patient number	-
4	Age	Actual value
5	Sex	Male, female
6	Start date of treatment	-
7	End date of treatment	-
8	Number of days from the start of treatment to discontinuation	-
9	Reason for discontinuation	Occurrence of an adverse event, unsatisfactory therapeutic effect, patient's refusal to receive Lipacreon, no visit, worsening of cystic fibrosis of the pancreas, other For "other," a specific reason for discontinuation will be presented.
10	Name of the adverse event as the reason for discontinuation	-
11	Seriousness	Non-serious, serious
12	Causal relationship with Lipacreon	Related, possibly related, unrelated, cannot be determined
13	Outcome	Resolved, resolving, not resolved, sequelae, fatal, unknown
14	Date of onset	-
15	Number of days to onset	-
16	Inclusion/exclusion of patient in the safety analysis	Included, excluded

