4.3.2.1. Changes over time in the nutritional endpoints

For patients included in the effectiveness analysis or patients included in the effectiveness analysis (patients completing the 52-week treatment), summary statistics for the actual measurement values of the nutritional endpoints by evaluation time point and changes in the nutritional endpoints from the start of treatment will be calculated. In addition, a paired t-test will be used to identify the presence or absence of any change in the nutritional endpoints from the start of treatment (Table 3.2.1.1, Table 3.2.1.2).

In addition, a line graph of the change in the mean value of each nutritional endpoint will be prepared (Figure 3.2.1.1, Figure 3.2.1.2).

No	Item name	Description
1	Nutritional endpoints	Body height (cm), body weight (kg), BMI, serum total protein (g/dL), albumin (g/dL), total cholesterol (mg/dL), triglycerides (mg/dL), hemoglobin (g/dL)

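### For nutrition and symptoms, SAP 3.6 has no row matching the protocol's Week-52-or-discontinuation time point; only the last evaluation combines early stoppers with continuing patients, and its cap is undefined and never Day 392.

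*SAP*

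**What the plan says.** **Protocol.** Sections 6(3) and 7 fix the main assessment: "Even if the administration period exceeded 52 weeks, the assessment is to be done at the time of 52nd weeks". The survey schedule in section 8 gives nutrition and symptoms one column for Week 52 or discontinuation. A separate column covers the end of follow-up (March 2018) or discontinuation during follow-up.

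**SAP 3.6, nutrition and symptoms.**
- Week 52: Day 364±28.
- Year X: Day 364×X±28, with X from 2 to 7.
- Discontinuation: "Date of discontinuation – 28 days to Date of discontinuation, which does not correspond to any of the above".
- Last evaluation: "Data obtained on the last date among the data obtained before Day" 364×X+28. No value or range of X is given in this row, and there is no lower limit.

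**SAP 3.6, overall improvement.** The last evaluation has a different rule: "All of the last dates".

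**SAP 4.3.2.1 and 4.3.3.1.** Results are given by evaluation time point. For nutrition, "a paired t-test will be used to identify the presence or absence of any change in the nutritional endpoints from the start of treatment". Frequency of defecation also has a paired t-test. The yes/no symptoms have a test the SAP spells McNamara, taken here as McNemar's. Neither section lists its time points, so I read them as those of 3.6, which include the last evaluation.

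**SAP 2.1.** Patients who stopped before Week 48 count as not completing 52 weeks, and the second effectiveness set contains only completers.

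**The concern.** The reasons for discontinuation in SAP 4.1.1.3 are "Occurrence of an adverse event, unsatisfactory therapeutic effect, patient's refusal to receive Lipacreon, no visit, worsening of cystic fibrosis of the pancreas, other". Several of these are related to the outcome. A Week 52 row that contains only patients still treated near Day 364 is therefore selected on doing well enough to stay on treatment, and completers are selected in the same way. A protocol column that joins Week 52 with discontinuation limits this selection, but the SAP has no row that does so.

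The last-evaluation row does bring the two groups together, but at different times. Stoppers contribute a first-year value. Continuing patients contribute a value from whenever their follow-up or the cap ends, which depends on the calendar date of entry. Height and weight are among the tested variables, and SAP 2.3 has age bands below 18 years, so growth accumulates in this row. The tested change then answers neither the 52-week question nor a defined long-term one.

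**Working it through.** **1. Longest follow-up.** SAP 1.2 gives "Survey period: August 30, 2011 through March 31, 2018". By the SAP's own duration rule (end − start + 1) this is 2406 days, or 2406/365.25 = 6.59 years. The SAP's last dose period, "At Year 7: Day 2185 to Day 2400", agrees to within 6 days.

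**2. Caps on the last evaluation, 364×X+28.**

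| X | Cap (day) | Years (÷365.25) |
|---|---|---|
| 1 (not in the stated range) | 392 | 1.07 |
| 2 | 756 | 2.07 |
| 3 | 1120 | 3.07 |
| 4 | 1484 | 4.06 |
| 5 | 1848 | 5.06 |
| 6 | 2212 | 6.06 |
| 7 | 2576 | 7.05 |

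The X = 2 cap is 756 − 392 = 364 days past the end of the Week 52 window. The X = 7 cap is 2576 − 2406 = 170 days past the longest follow-up, so it limits nothing.

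**3. Where a patient who stopped before Day 336 appears.**
- Week 52 (Day 336 to 392): no on-treatment value.
- Completer set: excluded, because Week 48 is Day 48×7 = 336.
- Discontinuation row: only if the final value fits no other window. The windows are Week 4 (Day 14 to 41), Week 8 (Day 42 to 70) and Week 24 (Day 140 to 196). A final value on Day 150 goes to Week 24, so this row does not collect all stoppers.
- Last evaluation: included, next to the later values of continuing patients.

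**4. Missing lower limit.** SAP 2.1 excludes a patient from the effectiveness set only if nutrition, symptoms and overall improvement after the start of treatment are all unavailable. A patient with baseline albumin, no later albumin and an overall rating stays in. Read literally, the baseline albumin is then the last value, and the change is zero.

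**5. How late the last values can be (assumption: uniform entry from 30 August 2011 to 31 March 2017, follow-up to 31 March 2018).** There are 2041 possible start days and 366 to 2406 days of follow-up, with mean (366 + 2406)/2 = 1386. The share followed beyond Day 392 is (2406 − 392)/2041 = 98.7%. With 20% or 30% stopping in the first year, 0.987×0.80 = 79% or 0.987×0.70 = 69% of last values can come from after Week 52. A steady drift in continuing patients enters at 1386/364 = 3.8 times its 52-week size if X = 7. If X = 2, the mean time is (391×561 + 1650×756)/2041 = 719 days, and the multiple is 719/364 = 2.0.

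**6. Selection in the Week 52 row.** Let a share d stop early and let continuing patients change by c. With zero change in stoppers, the all-patient change is (1 − d)c and the overstatement is 1/(1 − d) − 1. With half the change in stoppers, it is 1/(1 − 0.5d) − 1.

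| d | Stoppers: zero change | Stoppers: half change |
|---|---|---|
| 10% | 11% | 5% |
| 20% | 25% | 11% |
| 30% | 43% | 18% |

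**The case against.** A reader might infer that no 52-week analysis at all includes early stoppers. The documents do not support that. The protocol rates overall improvement at Week 24 and at Week 52 or discontinuation, with no rating in follow-up, and SAP 4.3.1.1 tabulates its last evaluation in the full effectiveness set. That is in effect a Week-52-or-discontinuation analysis with stoppers included. Patients who stop between Day 336 and Day 363 can also have a Week 52 value.

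A reader might also take 6.6 years and a 3.8-fold drift as what the SAP prescribes. Both need X = 7. The range 2 to 7 belongs to the Year X row, and the last-evaluation row does not say which X applies, or whether one or several do. With X = 2 the cap is about 2 years and the drift about 2.0-fold.

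Nor is a last evaluation in follow-up wrong in itself. The protocol's end-of-follow-up column gives it a basis for nutrition and symptoms. It also explains why the label reaches further there than for overall improvement.

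It is fair to add that Week 52 and each later year have their own rows, and that stoppers' values appear in the earlier rows or the discontinuation row. Individual values and dates are listed in Table 5.2.1.2. With 38 patients with cystic fibrosis cited over ten years (protocol section 2), such listings can be read patient by patient. The survey is uncontrolled and names no primary 52-week endpoint. These points limit the consequence. They do not supply the missing summary: a listing gives no mean change or test at the protocol's combined time point.

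**Conclusion.** The point holds for nutritional endpoints and symptoms, and for patients who stopped before Day 336. No tested row matches the protocol's Week-52-or-discontinuation time point. The one row that combines stoppers and continuing patients has an undefined X, no stated X that gives a 52-week cap, and no lower limit. These findings follow from the text alone.

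The size cannot be fixed from the documents, which give neither a stopping rate nor an entry pattern. Under the assumptions shown, the Week 52 available-case mean overstates the all-patient change by 11% to 43% (zero change in stoppers) or 5% to 18% (half the change) for 10% to 30% stopping. The direction also rests on stoppers doing worse than continuing patients, which is plausible from the listed reasons but not established. The 79% and 69% shares are upper limits, since follow-up beyond Day 392 does not guarantee a measurement. The change should be made, but it does not put the survey as a whole in doubt.

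**What to change.** In SAP 3.6, for nutrition and symptoms:

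1. Add a row for Week 52 or discontinuation: the latest value after the start of treatment and no later than Day 392, discontinuation values included. Report it with the paired t-test and McNemar's test in Tables 3.2.1.1 and 3.3.1.1, beside the Week 52 available-case row.
2. Keep the existing last-evaluation row as a separately labelled follow-up summary. State its X, restrict it to values after the start of treatment, and show the median and range of the evaluation day. Whether it keeps its test is a matter of preference.

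The cost is SAP wording and one extra row per table, with no new data. The new row carries stoppers' earlier values forward, so it still mixes times, but within Day 392 rather than over several years. The 52-week change may look slightly less favourable than the available-case figure.

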If dosage increase from usual daily dosage (1800mg) is to be done during the observation period or follow-up period, perform measurement of nutritious assessment items and monitor the symptoms relating to pancreatic exocrine insufficiency before the dosage increase. (Please refer 8. Items of registry (7) and (8))

[Precautions related to dosage and administration method]

In regarding to the adjustment of dosage and administration, age, weight, volume of meal, dietary and frequency of meal, etc. should be considered.

[Important Precaution]

In overseas, there were reports of stenosis of ileocecal area and colon (fibrosing colonopathy) in CF patients who have been administrated with high dosage of pancreatin products. So, careful observation should be provided and if any abnormality or change of abdominal symptom was found, appropriate action should be taken. Especially for patients with PEI due to CF, careful observation is necessary if patient is administered over 150 mg (equivalent to 1/2 sachet or one capsule) per kg body weight per day of Pancrelipase.

5. Number of planned institutions for registry by department

The registry will take place in departments of pediatric, internal medicine, digestive organs, and gastroenterology, etc. The number of the planned institutions is unknown because the contract will be signed after confirming the CF patient's availability in that institution.

6. Method of registry

(1) Request/Contract of the Registry

The target medical institutions are where LipaCreon is to be adapted/delivered and any CF patient is under or planning to be provided treatment. Medical Representative in charge of each medical institution explains to the doctors and relating people in charge, the purpose, target subjects and method of this registry sufficiently. In case the acceptance for the participation to this registry was obtained, he/she takes actions for the contract. The contract is to be signed between the head of medical institution and the sponsor in writing.

(2) Selection of target patients and registration

- 1) Prospective registry method is employed. It is an all cases registry.
- 2) Doctor in charge of this registry registers the patient is under or planning to be provided treatment by LipaCreon, by sending facsimile the registration form to the registration center. The registration form should include following items :
 - ① Patient ID No., ② Sex, ③ Date of birth or age,
 - ④ Inpatient/outpatient classification,

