6) Measure taken about the adverse event 7) Date of outcome (or outcome confirmation date) 8) Outcome 9) Causal relation to LipaCreon 10) Factors other than LipaCreon 11) Symptoms and history of adverse event 12) Laboratory test results related to the adverse event 13) Comment on the adverse event

(6) Events attributed to cystic fibrosis

Information regarding below items should be collected on the diseases, symptoms, signs or abnormal changes in laboratory test values which were attributed to the cystic fibrosis occurred after administration of LipaCreon.

- 1) Presence or absence of event attributed to cystic fibrosis
- 2) Name of event
- 3) Date of onset 4) Measure taken about the event
- 5) Date of outcome (or outcome confirmation date)
- 6) Outcome

(7) Nutrition assessment items

The following nutrition assessment items are determined before the start and after 4, 8 and 24 weeks from the start of administration of LipaCreon, at the end of observation period or at the time of discontinuation during observation period, and per year or at the end of follow-up period or at the time of discontinuation during follow-up period.

If the dosage increase from usual dosage (1800mg/day) is to be done during the observation period or follow-up period, perform assessment before the dosage increase.

- BMI (Height, body weight)
- Serum total protein
- Albumin
- Total cholesterol
- Triglyceride
- Hemoglobin

(8) Symptoms relating to pancreatic exocrine insufficiency

Following symptoms should be monitored at the timing before the start of administration, 4th, 8th, 24th week after administration started, and completion/discontinuation of follow-up during the observation period,

and per year or at the end of follow-up period or at the time of discontinuation during follow-up period. If the dosage increase from usual dosage (1800mg/day) is to be done during the observation period or follow-up period, those symptoms should be monitored before the increase will take place.

- Steatorrhea
- Frequency of defecation
- Diarrhea
- Bad odor of feces
- Appetite loss
- Abdominal distention

(9) Overall improvement rating

The overall improvement is assessed in the following 4 grades after 24 weeks from the start of administration of LipaCreon, and at the end of observation period at 52nd week or at the time of discontinuation.

Effective, unchanged, aggravation, unassessable

(10) Discontinuation

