When the administration is discontinued during the observation period, or when follow-up became impossible due to patient's visit stopped, or other reasons, the date of discontinuation and the reason for discontinuation is stated in the CRFs.

(11) Case of pregnancy

The information related to pregnancy is separately investigated in the pregnant case and the case whose pregnancy is found during the observation period at the point the pregnancy is known and after the birth of baby.

Survey schedule

Survey items	At the start of administration	Time point					
		During observation period				During Follow-up period	
		After 4 weeks	After 8 weeks	After 24 weeks	After 52 weeks or at the discontinuation	Per year	At the end of Follow-up Period (Mar. '18) or at the discontinuation
Registration	○						
Patient background	○						
Administration status of LipaCreon	○			○		○	○
Administration status of concomitant drug	○			○		○	○
Nutrition assessment items*	○	○	○	○	○	○	○
Symptoms relating to pancreatic exocrine insufficiency *	○	○	○	○	○	○	○
Overall improvement rating				○	○		
Reason for discontinuation					At the time of discontinuation ○		At the time of discontinuation ○
Adverse events	Investigation from the start of administration and throughout the observation period						
Events attributed to cystic fibrosis	Investigation from the start of administration and throughout the observation period						

* : If dosage increase from usual daily dosage (1800mg) is to be done during the observation period or follow-up period, perform measurement of nutritious assessment items and monitor the symptoms relating to pancreatic exocrine insufficiency before the dosage increase.

9. Timing, items and methods of analysis

(1) Timing of analysis

After 3 or 4 years from start of registry, the interim analysis is to be done.

And at the end of registry, the final analysis is to be done.

(2) Matters related to case formation

- Number of registered cases and number of cases from which the CRF is collected
- Number of cases accepted for safety and efficacy analysis
- Number of cases excluded from analysis and the reason for exclusion

(3) Matters related to safety

- Adverse reaction onset status
- Factors considered to have influence on the safety (The incidence of ADRs by patient background)
- Adverse event and serious adverse event

(4) Matters related to effectiveness

- Changes in nutrition assessment items
- Overall improvement rating

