1.3. Drug Product and its Dosage and Administration

Lipacreon® Granules 300 mg Sachets

Each sachet contains 300 mg of pancrelipase.

Lipacreon® Capsules 150 mg

Each capsule contains 150 mg of pancrelipase.

The usual dosage is 600 mg/dose of pancrelipase administered orally immediately after each meal three times daily. The dosage may be adjusted according to the condition of the patient.

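### The SAP's definition of a dose increase takes in the usual dose of 1800 mg/day, whereas the protocol's trigger is a rise above it

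*SAP*

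**What the plan says.** SAP 1.3 gives the regimen: "The usual dosage is 600 mg/dose of pancrelipase administered orally immediately after each meal three times daily". Protocol section 4 gives the same regimen and states the daily total as 1800 mg.

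The protocol ties an extra assessment to going beyond that dose. Section 4 sets the condition as "If dosage increase from usual daily dosage (1800mg) is to be done during the observation period or follow-up period", and section 8(7) on the nutrition items as "If the dosage increase from usual dosage (1800mg/day) is to be done during the observation period or follow-up period". Section 8(8) on symptoms and the footnote to the survey schedule repeat it. Each time, 1800 is the dose from which the increase starts.

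SAP 3.6 has a matching evaluation time point, *Before dose increase*, for the nutritional endpoints and the pancreatic symptoms. Its window is "Start date of dose increase – 28 days to Start date of dose increase". The table's second footnote defines the event: "A dose increase will be defined as a dose of ≥ 1800 mg/day administered".

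Two other parts of the SAP bear on the point. The dose categories in section 2.3 are "<900, 900, >900 and <1800, 1800, >1800, unknown/unspecified", so 1800 and anything above it are kept apart. Section 4.2.2.2 defines an increased pattern by comparing a patient's initial, lowest, maximum and last doses. That definition serves Table 2.2.2 only, and section 3.6 does not refer to it.

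**The concern.** The two documents place the usual dose on opposite sides of the line. Under the protocol, 1800 is the starting point of the increase; under the SAP, reaching 1800 is already the increase. The footnote also says nothing about a prior dose, so it does not settle whether a change is needed or which date applies if more than one dose qualifies.

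SAP 4.3.2.1 and 4.3.3.1 summarise the nutritional endpoints and symptoms by evaluation time point and test them against the start of treatment. The pre-increase row should describe patients just before they went above the usual dose. If it also holds patients who were only being brought up to the usual dose, it cannot be read that way.

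Such patients are plausible. The SAP has dose categories below 1800 and age and weight bands for small children, and the protocol tells physicians to adjust the dose for age and weight. The population is also very small: the protocol cites 13 patients reported in 2004 and 38 over the ten years from 1995. A few misplaced patients could change the row.

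**Working it through.** **Inputs.** Usual regimen: 600 mg three times daily (Protocol 4, SAP 1.3). Protocol trigger: an increase from 1800 mg/day (Protocol 4, 8(7), 8(8), survey schedule footnote). SAP rule: a dose of at least 1800 mg/day (SAP 3.6, second footnote). The plan gives no numerical result to reproduce here.

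**Step 1, the threshold.** 600 mg × 3 = 1800 mg/day. The SAP limit equals the usual dose and includes it. An increase from 1800 means a dose above 1800.

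**Step 2, the rules applied to example dose courses (mg/day).** The SAP rule is read in two ways: as a rise that reaches the limit, and literally as any dose at or above it.

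| Course | Protocol trigger | SAP, as a rise reaching 1800 | SAP, literal |
|---|---|---|---|
| 900 to 1800 | No | Yes | Yes |
| 1800 throughout | No | No | Yes, Day 1 |
| 2400 throughout | No | No | Yes, Day 1 |
| 1800 to 2400 | Yes, at the change | Yes, at the change | Yes, but could be dated Day 1 |
| 900 to 1800 to 2400 | Yes, at the change to 2400 | Yes, at 1800 or at 2400; no rule to choose | Yes, from the date 1800 is reached |

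The first course departs from the protocol on both readings.

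**Step 3, how a patient without the trigger gets a value.** The window reaches back 28 days, so routine visits can fill it. For a change from 900 to 1800 on Day 56, it runs from Day 56 − 28 = Day 28 to Day 56. The specified dates for Week 4 (Day 28) and Week 8 (Day 56) both lie inside it. The patient enters the row although the protocol asked for no pre-increase assessment.

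**Step 4, the Day 1 case on the literal reading.** With an increase on Day 1 the window is Day −28 to Day 1. This lies inside the baseline window (up to Day 1), and the specified date is the same. A latest baseline value from those days would be reused as the pre-increase value, with a change of zero.

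**Step 5, reach.** There are 8 nutritional endpoints and 6 symptoms (5 present/absent symptoms plus defecation frequency): 8 + 6 = 14 endpoints. In two analysis sets this gives 14 × 2 = 28 tests at this time point. That is an upper bound, because the SAP does not list which time points are tested.

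**The case against.** The strongest reply is that little depends on this row. This is an all-case registry with no designated primary test and with unadjusted 5% tests (SAP 3.2). Overall improvement, the effectiveness rate, adverse drug reaction incidence and the dose-pattern table do not use the footnote. Table 5.2.1.1 lists doses with dates, and Table 5.2.1.2 gives test dates and values for 13 of the 14 endpoints (diarrhea is not listed), so much of the row can be checked by hand. All of this stands and limits the weight of the point, but it does not make the rule right. The ≥ sign may also be a slip for >, given the categories in SAP 2.3. The documents do not settle that, and a slip would still need correcting before programming.

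Two stronger readings are tempting.

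- **A reader might infer that every patient who starts at 1800 will be counted as having an increase.** The row label and the phrase for its start date both imply a change in dose, so this reading is strained. It remains only as something a programmer could do, because the definition itself does not require a change.
- **A reader might infer that the footnote also corrupts the discontinuation row**, which takes "Date of discontinuation – 28 days to Date of discontinuation, which does not correspond to any of the above" and stands below the pre-increase row. The documents support this only narrowly. Every day shared by the two windows falls on or before the rise. The protocol requires an assessment at discontinuation, and SAP 3.6 adopts the value nearest the specified date. A value recorded after the rise therefore stays in the discontinuation row and would be preferred anyway. The result can change only if that required assessment is missing, or if the rise and the discontinuation fall on the same day. The exclusion would also apply to true rises above 1800 under a corrected definition, so it is not specific to the ≥ sign.

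**Conclusion.** Wrong as written; low impact. The SAP's rule conflicts with a condition that the protocol states in four places, and nothing else in either document reconciles them. The certain consequence is that a rise ending at exactly 1800 counts as a dose increase, so the row mixes patients with and without the protocol's trigger. Flagging of starting doses, or dating a true rise at Day 1, is possible under the wording but not certain.

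The effect is confined to one supplementary time point. The number of patients cannot be stated, since it depends on how many are brought up to exactly 1800 and the documents give no dose distribution. The conclusion assumes that an increase from 1800 means a move to a dose above 1800, which is the plain sense of the protocol's wording.

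**What to change.** Replace the footnote with a definition based on change: a dose increase is a change, after the start of treatment, from a daily dose of ≤1800 mg/day to one of >1800 mg/day, dated at that change. If there are several such changes, use the first. State that rest periods are ignored when doses are compared, so that a restart at the same dose is not an increase.

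For the courses in the table, 900 to 1800 and both constant courses then give no increase. The courses 1800 to 2400 and 900 to 1800 to 2400 each give one, dated at the change to 2400. The definition also counts a direct move from below 1800 to above it, which goes slightly beyond the protocol's literal wording. The sponsor should confirm that choice, and whether further rises from a dose already above 1800 also count. If the sponsor in fact wants any rise to 1800 to qualify, the protocol and SAP should be aligned on that.

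The cost is one footnote and a sentence on repeated increases. The dose dates and assessments are already collected, and the SAP's dose categories already separate 1800 from higher doses.
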